9.2. Benefit / Risk Information

9.2.1. Potential risk(s) related to the study drug

Common and important adverse reactions associated with IVIg administration are described in the European Guideline EMA/CHMP/BPWP/94038/2007 rev.4 of IVIg [[14](#)].

Adverse reactions such as chills, headache, dizziness, fever, vomiting, allergic reactions, nausea, arthralgia, low blood pressure and moderate low back pain may occur occasionally with IVIg.

Rarely human normal Ig may cause a sudden fall in blood pressure and, in isolated cases, anaphylactic reaction, even when the patient has shown no hypersensitivity to previous administration.

Cases of reversible aseptic meningitis and rare cases of transient cutaneous reactions have been observed with human normal immunoglobulin. Reversible haemolytic reactions have been observed in patients, especially those with blood groups A, B, and AB. Rarely, haemolytic anaemia requiring transfusion may develop after high dose IVIg treatment.

Increase in serum creatinine level and/or acute renal failure have been observed.

Very rarely, thromboembolic reactions such as myocardial infarction, stroke, pulmonary embolism, deep vein thromboses have been described.

Important potential risks that could be anticipated with I10E administration are those known with IVIg preparations:

Hypersensitivity

True hypersensitivity reactions are rare. They can occur in patients with anti-IgA antibodies.

Rarely, human normal immunoglobulins can induce a fall in blood pressure with anaphylactic reaction, even in patients who had tolerated previous treatment with human normal immunoglobulins.

To minimize risk of anaphylactic reactions, patients with IgA deficiency will be excluded, except if the absence of anti-IgA antibodies is documented [37] [38]. The patients with a known hypersensitivity to the active substance or to any of the excipients of I10E will be excluded.

Thromboembolism

There is clinical evidence of an association between IVIg administration and thromboembolic events such as myocardial infarction, cerebral vascular accident (including stroke), pulmonary embolism and deep vein thromboses. Such an association is assumed to be related to a relative increase in blood viscosity through the high influx of immunoglobulins in at-risk patients.

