To minimize the risk of thromboembolic events, patients with a history of venous thromboembolic disease, myocardial infarction or cerebrovascular accident will be excluded. As well, patients with uncontrolled cardiac arrhythmia and patients with unstable ischemic heart disease will not be allowed to participate to the study.

Acute renal failure

Cases of acute renal failure have been reported in patients receiving IVIg therapy. In most cases, risk factors have been identified. These included pre-existing renal insufficiency, diabetes mellitus, hypovolaemia, overweight, concomitant nephrotoxic medicinal products and age over 65.

To minimize the risk of acute renal failure, patients with a chronic kidney disease (CKD) defined as abnormalities of kidney structure or function, present for >3 months, with implications for health, i.e. patients with persistent albuminuria category A3 and/or GFR <60 mL/min/1.73m² (measured according to the MDRD calculation) will be excluded [39].

The use of loop diuretics is also not allowed if used within 24 hours prior to study drug administration.

Aseptic meningitis syndrome (AMS)

Aseptic meningitis syndrome has been reported to occur in association with IVIg treatment.

Discontinuation of IVIg treatment has resulted in remission of AMS within several days without sequelae. AMS may occur more frequently in association with high-dose of IVIGs.

Haemolytic anaemia

IVIg products can contain blood group antibodies which may act as haemolysins and induce in vivo coating of red blood cells with immunoglobulin, causing a positive direct antiglobulin reaction (Coombs' test) and, rarely, haemolysis. Haemolytic anaemia can develop subsequent to IVIg therapy due to enhanced red blood cells (RBC) sequestration.

Haptoglobin and LDH levels in patients will be assessed at every visit.

Interference with serological testing

After injection of immunoglobulin the transitory rise of various passively transferred antibodies in the patient's blood may result in misleading positive results in serological testing.

Passive transmission of antibodies to erythrocyte antigens, e.g. A, B, D may interfere with some serological tests for red cell antibodies for example the direct antiglobulin test (DAT), direct Coombs' test.

Interaction with other medicinal products

I10E may impair the efficacy of live attenuated virus vaccines for a period of up to 3 months. In the case of measles, this impairment may persist for up to 1 year.

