4.7. Safety Analyses

Safety analyses will be conducted on the TTS. All safety analyses will be performed on the subgroups of relapsing Ig-pretreated patients and Ig-naïve patients as well as overall.

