- TEAE = “Yes” if AE onset date = start date of first IMP infusion and investigator’s assessment of the time of onset ≠ “Before infusion”
- TEAE = “No” otherwise
- If the date of AE onset is a partial date and the investigator’s assessment of the time of onset is not missing: TEAE = “Yes” if investigator’s assessment of the time of onset “During infusion”, “≤72h” or “>72h”
- If the date of AE onset is a partial date and the investigator’s assessment of the time of onset is missing:
 - TEAE = “Yes” if last possible date in the period defined by the partial date ≥ start date of first IMP infusion / “No” if the last possible date in the period defined by the partial date < start date of first IMP infusion
- TEAE = “Yes” otherwise

Temporally associated adverse events (TAAEs)

TAAE will be defined according to the item “Schedule” collected in the eCRF. They will include all adverse events with Schedule “During infusion”, “Within 72 hours after the end of the infusion”. If Schedule is missing then the event will be classified as TEAE by default.

Other significant AEs

Other Significant AEs are based on the definition of relevant AESIs (Adverse Events of Special Interest) for I10E. They are defined as standardized MedDRA queries (SMQs) of interest on the narrow scope, these are:

- Anaphylactic reaction (SMQ) [20000021] narrow scope
- Anaphylactic/anaphylactoid shock conditions (SMQ) [20000071] narrow scope
- Noninfectious meningitis (SMQ) [20000134] narrow scope
- Embolic and thrombotic events, vessel type unspecified and mixed arterial and venous (SMQ) [20000083] narrow scope
- Acute renal failure (SMQ) [20000003] narrow scope
- Hemolytic disorders (SMQ) [20000019] narrow scope
- Eosinophilic pneumonia (SMQ) [20000157] narrow scope
- Interstitial lung disease (SMQ) [20000042] narrow scope

Pre-treatment Adverse Events

Pre-treatment AEs will be listed for all enrolled patients.

Summary of treatment Emergent Adverse Events (TEAE)

A summary of the total number of TEAEs, and number and percentage of patients with at least one TEAE will be presented. This summary will include the number and percentage of patients having at least one TEAE as well as the absolute number of TEAEs in each AE category:

- TEAEs
- Serious TEAEs by seriousness criterion

- Drug-related TEAEs
- TAAEs
- TEAEs by severity (Mild / Moderate / Severe)

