- TEAEs by Action taken with IMP (None / Dose reduced / Dose increased / Discontinuation of IMP / Temporary interruption of IMP, (the action could also be a decrease of infusion flow rate))
- TEAEs by outcome (Resolved without sequelae / Resolved with sequelae / Not recovered / Recovering / Fatal / Unknown)
- Other significant AEs

A similar summary table will be produced for TAAEs as well as drug-related TEAEs and Serious TEAEs.

All TEAEs, SAEs, TAAEs and drug-related AEs will be summarized by SOC and PT, showing number of TEAEs, and number and percentage of patients with at least one TEAE, sorted by decreasing incidence of SOC and PT within SOC in the column “overall”.

Summary of TEAEs will also be presented by relevant subgroups (e.g., by age group [<65 years and ≥ 65 years], sex, race [white, non-white and unknown], and BMI [<30 kg/m² and ≥ 30 kg/m²]).

The rate of TEAEs by patient, course, infusion and drug-related AEs by course will be presented and sorted by decreasing incidence of PT in the column “overall”. Rate is defined as the number of events for unique PTs divided by the total number of patients, courses and infusions respectively.

Duration of most-common (those which occurred in at least 10% of the patients in the overall safety population) drug-related AEs will be calculated as is outlined in Section [5.7.2](#) and will be presented with descriptive statistics on recovered AEs (i.e., AEs with an outcome of “Recovered without sequelae” or “Recovered with sequelae”). Statistical unit of analysis will be the individual who recovered from drug-related AE. No imputation will be performed for the purposes of computing duration.

The time between the stop time of the last administration of IMP (before the onset of event) to the onset of the drug-related AEs will be calculated (in days) as is outlined in Section [5.7.2](#) and will be presented with descriptive statistics using the individual drug-related AE as statistical unit.

All Serious TEAEs, drug-related AEs, AEs leading to dose changes (action taken is not missing, “None” or “Not-applicable”) or discontinuation of IMP, and other significant TEAEs will be listed. These listings will include the event duration as well as the time elapsed (in days as is outlined in Section [5.7.2](#)) between the stop time of the last administration to the onset of the event.

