Change from before start of the course to time points b) and c) will be presented as well.

A graphical display of the evolution pre-dose values (before IMP infusion) of each vital sign parameter over time (by course). The evolution of (before start of the course, time points b) and c) at each day) will be also presented with connected box-and-whisker plots by course. The number of observations at each visit will be displayed in all graphs.

All abnormalities, clinically significant or not, will be listed in both patient level and course/infusion level formats. If a patient assessment has no timepoint attributed then these assessments are classified as unscheduled.

4.7.3. 3. *Thrombo-embolic physical examination*

Number and percentage of patients with at least one abnormal thrombo-embolic sign will be presented by visit together with the absolute number of signs for the following:

- Arterial thrombo-embolic signs
- Venous thrombo-embolic signs

4.7.3. 4. *Complete physical examination*

Physical examination results will be listed.

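### The only thromboembolic query in the SAP's special-interest AE category is titled for unspecified or mixed vessel type, so by its wording a deep vein thrombosis or myocardial infarction would not be counted there

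*SAP*

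**What the plan says.** SAP 4.7.2 ties the category of other significant AEs to the sponsor's adverse events of special interest for I10E and then fixes its content: "They are defined as standardized MedDRA queries (SMQs) of interest on the narrow scope, these are", followed by eight queries. One of the eight is thromboembolic: "Embolic and thrombotic events, vessel type unspecified and mixed arterial and venous (SMQ) [20000083] narrow scope". The other seven cover anaphylaxis (two queries), non-infectious meningitis, acute renal failure, haemolysis, eosinophilic pneumonia and interstitial lung disease.

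The category is one line in the TEAE summary, and "A similar summary table will be produced for TAAEs as well as drug-related TEAEs and Serious TEAEs". It also defines a listing: AEs leading to dose changes "or discontinuation of IMP, and other significant TEAEs will be listed". Under SAP 4.7, "All safety analyses will be performed on the subgroups of relapsing Ig-pretreated patients" as well as on Ig-naïve patients and overall.

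On the risk itself, Protocol 9.2.1 refers to "thromboembolic events such as myocardial infarction, cerebral vascular accident (including stroke), pulmonary embolism and deep vein thromboses" and says that, to reduce that risk, "patients with a history of venous thromboembolic disease, myocardial infarction or cerebrovascular accident will be excluded". SAP 4.7.3.3 plans a separate display of examination findings: "Number and percentage of patients with at least one abnormal thrombo-embolic sign will be presented by visit", with arterial and venous signs shown apart.

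**The concern.** A special-interest category exists to bring together the events that matter most for the product, so that a reader need not search the full SOC/PT tables. Here the protocol's named thromboembolic events and the query meant to collect them do not match. The query's title restricts it to events not assigned to one vessel type, while at least two of the protocol's four examples have a definite vessel type.

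The trial gives this risk real weight. Exclusion criteria 6, 8 and 9 in Protocol 5.2.2 concern thrombosis, thrombophilia and venous stasis. A focused thromboembolic examination is planned before each course from Visit 4 to Visit 10. D-dimers are tested when venous thrombosis is suspected (Protocol 8.3).

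The SAP plans no other grouped count of thromboembolic AEs. A zero on the special-interest line could therefore be read as no thromboembolic event, when it means only that no event matched this one query.

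**Working it through.** The plan states no figure on this point, so there is nothing to reproduce. The check compares passages, followed by simple arithmetic for size.

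**1. Is the list closed?** Yes. SAP 4.7.2 introduces it as a full definition, with no open-ended wording. Of the eight queries, one is thromboembolic by title. None is titled arterial, none venous, and none covers all embolic and thrombotic events. By title, none of the other seven would pick up a clot or an infarct.

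**2. Do the protocol's named events fit the title?**

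| Event named in Protocol 9.2.1 | Vessel type | Within the title (unspecified or mixed)? |
|---|---|---|
| Deep vein thrombosis | Venous by name | No |
| Myocardial infarction | Arterial | No |
| Stroke | Depends on MedDRA content not in the documents | Cannot be settled |
| Pulmonary embolism | Depends on MedDRA content not in the documents | Cannot be settled |

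At least 2 of the 4 fall outside. The words arterial and venous at the end of the title qualify mixed; they do not turn the query into one for all arterial and all venous events.

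**3. How are the other protocol risks treated?** Acute renal failure, aseptic meningitis and haemolytic anaemia, all in the same protocol section, each have a query whose title is not limited to a sub-type.

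**4. Which outputs are affected?** The special-interest line of the TEAE summary, and the same line of the TAAE, drug-related and serious summaries if it is carried over: up to 4 tables. The listing of other significant TEAEs adds 1.

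**5. What does one missed patient change?** The SAP plans a single pooled line with no stated breakdown by query, so a thromboembolic rate cannot be bounded. On the pooled line:

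- Overall, with the planned 42 patients: 1/42 = 2.4 percentage points, and the event count is one too low.
- By subgroup, assuming a one-third/two-thirds split: 42/3 = 14 and 42 − 14 = 28, giving 1/14 = 7.1 points in the smaller column or 1/28 = 3.6 points in the larger. The documents say around one third without saying which group that is.
- If the patient already counts under another listed query, the percentage does not change; only the event count does.

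**The case against.** The strongest counter-argument is that neither document reproduces the terms in the query, so the exclusion is inferred from a title. The vessel type of myocardial infarction is also the reviewer's classification, because the protocol does not assign one. This stands as a limit on certainty and is why the terms must be checked against MedDRA 17.1. It does not rescue the plain reading, least of all for deep vein thrombosis.

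Second, the SAP bases the list on the sponsor's special-interest definition, which is not supplied, and the list does not simply mirror Protocol 9.2.1: it adds two lung conditions that section does not name. A deliberate choice cannot be ruled out, but no reason is given. Silence in SAP 4.10 is weak evidence, because that section records changes from the protocol and the protocol defines no such category.

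Third, hypersensitivity is also covered only by the two anaphylaxis-titled queries, so thromboembolism may not be the only risk with a narrow query. That weakens the inference of an oversight without supplying the missing count.

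Fourth, no event is lost. It stays in the SOC/PT tables and, under SAP 5.1, in the general patient listings. If serious, drug-related, or leading to a dose change or discontinuation, it is also listed individually with the same content. Protocol 9.2.1 describes these reactions as very rare and the trial excludes patients at high risk, so there may be no affected event at all. All of this stands. It limits the size of the problem to a descriptive count and flag.

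**Conclusion.** The concern holds. Applied as written, the SAP's rule leaves events of a single vessel type out of its special-interest category, although the protocol names such events under an important potential risk. At least two of the four named events are affected, in up to four summary lines and one listing. Each missed patient costs 2.4 percentage points on the pooled line.

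Confidence is medium. The conclusion assumes that the query's content follows its title and that the planned 42 patients are treated; the subgroup figures also assume the 14/28 split. The primary efficacy analysis and expedited reporting are unaffected. The point should be fixed because a stated rule gives an incomplete safety count, but it does not threaten the trial's main conclusion.

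**What to change.** Before database lock, redefine the thromboembolic part of the category so that it covers arterial events and venous events as well as those of unspecified or mixed vessel type, all at narrow scope. Confirm the resulting term list against MedDRA 17.1, the version named in SAP 4.7.2, and settle there where stroke and pulmonary embolism fall. Summarise the thromboembolic events together so that they can be read apart from the pooled line. Record the change in SAP 4.10.2. If the sponsor intends the restriction, the SAP should say so and give the reason.

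If the database is already locked, the same count can be added as a labelled supplementary summary.

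The cost is one SAP line, a longer term list and one dictionary check. If the sponsor's special-interest definition for I10E uses the same single query, it has to be aligned too. No new data are needed.

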3.1.4. Treatment

Patients who meet all the eligibility criteria will receive one dose of study drug at 2 g/kg over 2 to 5 days. Three (3) weeks later, they will start to receive 7 doses of study drug at 1 g/kg over 1 to 2 day(s) each, every 3 weeks (+/- 7 days).

Investigators or Study Nurses will call patients 4 days (+/-1 day) after the end of each study treatment course to document potential AEs and TAAEs (see Section [8.2.4](#)).

Duration of the treatment period will be approximately 21 weeks.

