12.10.1. Adverse events

All AE will be classified using MedDRA including Lowest Level Terms (LLT), Preferred Terms (PT) and System Organ Class (SOC).

TEAEs defined as AEs occurring after the start of the 1st study drug administration will be analysed. Other AEs will only be listed.

The absolute number of TEAEs as well as the number of patients with at least one TEAE will be tabulated by SOC and PT. Patients with SAEs, drug-related AEs will be analysed by SOC and PT.

The duration of the TEAE and the time between the last administration of study drug and the onset of the TEAE will be calculated.

TAAEs will be analysed by patients and infusions.

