2.5.3. Safety criteria

The safety criteria include:

- Treatment emergent adverse events (TEAEs)
- Serious adverse events (SAEs)
- Temporarily associated adverse events (TAAEs), i.e., AEs that begin during an infusion or within 72 hours after an infusion
- Clinically significant changes from baseline in vital signs
- Clinically significant changes from baseline in laboratory parameters

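### The protocol's by-infusion analysis of temporally associated adverse events is missing from the SAP and not declared as a change

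*SAP*

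**What the plan says.** TAAEs are a safety endpoint in the protocol (synopsis and 3.2.3). SAP 2.5.3 defines them as "AEs that begin during an infusion or within 72 hours after an infusion". Protocol 12.10.1 fixes the units of analysis: "TAAEs will be analysed by patients and infusions".

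SAP 4.7.2 shows TAAEs in three places:
- as a line in the overall TEAE summary, with events and patients;
- in a summary of their own: "A similar summary table will be produced for TAAEs as well as drug-related TEAEs and Serious TEAEs";
- by system organ class and preferred term: "All TEAEs, SAEs, TAAEs and drug-related AEs will be summarized by SOC and PT, showing number of TEAEs, and number and percentage of patients".

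The same section specifies rates with other denominators: "The rate of TEAEs by patient, course, infusion and drug-related AEs by course will be presented". It explains them so: "Rate is defined as the number of events for unique PTs divided by the total number of patients, courses and infusions respectively". A further table gives drug-related TEAEs by course number. None of these rates names TAAEs.

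SAP 4.10.2 declares two safety changes from protocol, the timing of vital signs and an added haemolysis analysis. TAAEs are not mentioned.

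On the schedule, Protocol 3.1.4 states that patients "will receive one dose of study drug at 2 g/kg over 2 to 5 days", followed by "7 doses of study drug at 1 g/kg over 1 to 2 day(s) each". The compliance rule in SAP 4.5.1 accepts 1 to 3 days for the later courses.

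**The concern.** The protocol commits to two units of analysis for this endpoint, and the SAP carries over one. The SAP has a section for declaring such differences and does not use it here, so a reader cannot tell whether the by-infusion analysis was dropped on purpose or overlooked.

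Safety is the trial's only secondary objective. Protocol 10.2 says that the telephone call four days after each course exists to capture TAAEs. With no control arm, TAAEs are also the event class defined by timing alone, without an open-label judgement of relatedness. As planned, the report would not show what proportion of infusions or courses was followed by a TAAE, or whether the first course at 2 g/kg differs in this respect from the later courses at 1 g/kg.

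**Working it through.** The plan states no TAAE rate, so there is no figure of its own to reproduce. The check is what each planned table covers, and then how large the denominators are and how they behave.

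**1. Coverage of the SAP 4.7.2 displays**

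| Display | Events | Patients | Courses | Infusions | By course number |
|---|---|---|---|---|---|
| Overall summary line, own summary, SOC/PT table | TAAEs | yes | no | no | no |
| Rate by preferred term | all TEAEs | yes | yes | yes | no |
| Rate by preferred term | drug-related AEs | no | yes | no | no |
| Rate by course number | drug-related TEAEs | those treated at that course | – | no | yes |

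No row combines TAAEs with an infusion or course denominator.

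**2. Size of the denominators**

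Inputs are 42 patients (Protocol 5.1), 8 courses, and the course durations in Protocol 3.1.4 and SAP 4.5.1. Assume one infusion per infusion day and all courses given.

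Infusions per patient = first-course days + 7 × later-course days.
- Protocol minimum: 2 + 7 × 1 = 9, so 42 × 9 = 378 infusions.
- Protocol maximum: 5 + 7 × 2 = 19, so 42 × 19 = 798.
- SAP 4.5.1 maximum: 5 + 7 × 3 = 26, so 42 × 26 = 1,092.
- Courses: 42 × 8 = 336, whatever the split.

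**3. How the rates respond to the split**

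The number of TAAEs is unknown. For assumed totals of 50, 100 and 200 events:

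| Events | Per patient (÷ 42) | Per 100 courses (÷ 336) | Per 100 infusions (÷ 378 / 798 / 1,092) |
|---|---|---|---|
| 50 | 1.19 | 14.9 | 13.2 / 6.3 / 4.6 |
| 100 | 2.38 | 29.8 | 26.5 / 12.5 / 9.2 |
| 200 | 4.76 | 59.5 | 52.9 / 25.1 / 18.3 |

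For a given number of events, the per-infusion rate changes by a factor of 798/378 = 2.1 within the protocol's range, and 1,092/378 = 2.9 up to the SAP limit. The patient and course rates do not move.

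**4. Why the TEAE-per-infusion rate is no substitute**

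Take consecutive infusion days and ignore infusion hours. A course of d days then has a TAAE window of (d − 1) + 3 days.
- Protocol minimum: 4 + 7 × 3 = 25 days.
- Protocol maximum: 7 + 7 × 4 = 35 days.
- SAP maximum: 7 + 7 × 5 = 42 days.

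From first infusion to the end-of-study visit is nominally 24 × 7 = 168 days. The window covers 25/168 = 15% to 35/168 = 21% of that time (42/168 = 25% at the SAP limit). Most of the time over which TEAEs are counted therefore lies outside it.

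**5. How far the split can move the patient percentage**

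The split can lengthen the window. With an assumed constant background event rate λ per day, P(at least one TAAE) = 1 − exp(−λ × window):

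| λ per day | 25 days | 35 days | 42 days |
|---|---|---|---|
| 0.005 | 12% | 16% | 19% |
| 0.01 | 22% | 30% | 34% |
| 0.02 | 39% | 50% | 57% |

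**The case against.** The strongest reply is that little is lost. The SAP gives TAAE event counts overall and by preferred term, and SAP 4.7.1 reports total infusions for course 1, for later courses and for all courses. Dividing one by the other yields a crude TAAE rate per infusion. Drug-related TEAEs are tabulated by course number, all data are listed, and safety analyses are descriptive. Protocol 12.2 leaves technical detail to the SAP and sends changes to the study report. The protocol asks for neither a course-level analysis, nor a split of course 1 from later courses, nor clustered intervals.

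Much of this stands. The crude overall rate is obtainable, so the information is not wholly absent. The course-level display and any interval adjusted for clustering go beyond what the protocol promised.

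Two things do not follow. First, event counts do not show how many infusions or courses had at least one TAAE, because one infusion may carry several events. Nor are TAAE counts broken down by course, so course 1 cannot be set against later courses. The by-course-number table does so only for events judged drug-related. Second, the allowance in Protocol 12.2 does not explain why SAP 4.10, which exists to record changes from protocol, is silent on this one.

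**Conclusion.** The point holds as an undeclared omission. An analysis that the protocol specifies for a named safety endpoint is not in the SAP, and the planned tables replace it only in part. It is a modest matter of completeness and consistency, with no bearing on the primary efficacy test.

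A reader might infer more: that leaving out the by-infusion table makes the patient-level figure depend on how many days each site used for a course. The documents do not support that. The patient denominator is fixed. The split can reach the patient percentage through the longer 72-hour window (step 5), but that happens whether or not the table is produced. The by-infusion rate is the measure whose denominator changes directly with the split (step 3), so restoring it would not remove the dependence.

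Nor can a spread in patient percentages be derived from a fixed risk per infusion. The documents give no such risk. The planned course dose does not depend on the number of days, so more infusion days mean less drug per infusion, and a constant risk cannot be presumed.

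The denominators assume completers, one infusion per infusion day, and all patients at one end of the permitted range. The event totals and background rates are assumed for illustration.

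**What to change.** Add to SAP 4.7.2:
- the number and percentage of infusions with at least one TAAE, which restores the protocol's analysis;
- the number and percentage of courses with at least one TAAE;
- both of these overall and for course 1 versus courses 2 to 8, beside the number of infusions per course, so that the per-infusion figure can be read against how courses were split.

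Assign each event to the most recent infusion. SAP 5.7.2 already measures onset from the previous infusion, and SAP 4.7.1 and 5.7.3 already derive infusion counts. A rule is needed for TAAEs flagged without a complete onset date, for instance counting them separately as unassigned. A confidence interval that treats the patient as the cluster is optional. If the sponsor prefers not to add the analysis, SAP 4.10.2 should declare and justify its removal.

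The later-course duration in Protocol 3.1.4 (1 to 2 days) and SAP 4.5.1 (1 to 3 days) must also be reconciled, since it sets the range of the infusion denominator.

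The cost is one SAP paragraph, one table and the assignment rule, using data already collected.
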